11.7.1.4 Definition of Type of Analysis

Analysis of safety variables will be based on the observed case analysis (no imputation at all).

11.7.2 Statistical Methodology

Descriptive statistics including the mean, median, standard deviation, minimum, and maximum will be presented for continuous variables. These statistical parameters, plus coefficient of variation and confidence intervals, will be used to describe bismuth plasma and whole blood

concentrations. For categorical variables, the number of subjects as well as the percentage within each category will be presented.

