
Study Procedures:
	
This is a single-arm, open-label trial in presumed H. pylori-positive subjects and is restricted to centers in France.
 
Following identification of participating general practice and specialist study centers, subjects deemed eligible for study will be identified and may be enrolled. To assess eradication, subjects will complete a diagnostic H. pylori test (breath test, biopsy, or other test at the discretion of the Investigator) following a period of at least 28 days after the end of treatment.
 
Subjects who are treatment-eligible will already have a prescription for Pylera® and a PPI (presumed to be omeprazole) and will have been instructed on dosing as the dosing information contained within the Pylera® SmPC: 3 capsules Pylera® QID taken after meals and following a bedtime snack, and omeprazole capsule BID taken after breakfast and evening meal doses of Pylera®, for 10 days (equivalent to daily doses of 480 mg [as Bi₂O₃ equivalent], tetracycline hydrochloride 1500 mg, metronidazole 1500 mg, and omeprazole 40 mg).
 
Subjects will provide two blood samples for assessment of bismuth concentrations (total bismuth in plasma and whole blood and trimethylbismuth (TMB) in whole blood), with one sample provided prior to start of Pylera® treatment (D0) and one sample provided Day 11 i.e. Day 1 after completion of Pylera® treatment. If accumulation of bismuth is detected (defined as whole blood bismuth concentration exceeding 50 µg/L.), subjects will be contacted to immediately return to the laboratory to draw a third verification sample and will be referred for potential inclusion and follow-up in a separate intensive monitoring program. In case of a neurological AE indicative of bismuth encephalopathy (please refer to Appendix 3 – Central Nervous System Adverse Events of Interest) is present at Day 11 blood samples will be as quickly processed as possible.

	
A diagnostic H. pylori test to assess H. pylori eradication should be repeated on one single occasion at least 28 days post-treatment.

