2 OBJECTIVES

2.1 PRIMARY OBJECTIVE

To verify the absence of accumulation of bismuth in subjects prescribed Pylera®, a pharmacokinetic approach in a real-life setting.

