11.7.4.2 Secondary Efficacy Endpoints

The eradication rate of Pylera®, defined as the proportion of negative test of diagnostic *H. pylori* test (breath test, biopsy, or other test at the discretion of the Investigator) conducted at least 28 days following the end of treatment with Pylera®, will be calculated, including a 95% confidence interval. The eradication rates will be calculated for both the Safety and Per Protocol Populations.

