An additional comparison will be made of all post-treatment concentrations in the omeprazole group versus post-treatment concentrations of all other PPIs pooled together. For each subject the C_{\min} will be grossly estimated assuming an elimination half-life of 19.95 hours³⁰ by the equation:

$$C_{\min} = \frac{C_{\text{observed}}}{e(-0.0347 * t)}$$

where t is the time elapsed between last dose intake and sampling time.

Individual observed results will also be classified as “above” or “below” the Hillemand *et al.*²⁷ alert threshold of 50 µg/L²⁷ for total whole blood bismuth concentrations solely as TMB has been calculated by Aptalis Pharma US, Inc. to exist at approximately 1:10,000 the level of average circulating bismuth concentrations.

For subjects who are already below 50 µg/L on Day 11, no other action will be performed and such subjects will be considered to have reached safe whole-blood levels within an acceptable time.

For subjects who are above 50 µg/L, the time required to reach 50 µg/L will be grossly estimated, again assuming an elimination half-life of 19.95 hours by the equation:

$$T_{recov} = \frac{\ln\left(\frac{50}{C_{min}}\right)}{-0.0347}$$

Such subjects will also be referred for evaluation and potential inclusion in the separate Intensive Monitoring Program.

The number of subjects requiring more than 24 hours to reach safe levels and the time required will be considered to draw conclusion on the clinical safety of Pylera® with regard to bismuth toxicity.

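### The proportion of subjects above 50 µg/L, which bears on the claim of no bismuth accumulation, is planned without a confidence interval, so a count of zero would be reported without the upper limit it supports

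*Protocol*

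**What the plan says.** - **Objective (Protocol 2.1):** "To verify the absence of accumulation of bismuth in subjects prescribed" Pylera.
- **Definition of accumulation (Synopsis, Study Procedures):** "defined as whole blood bismuth concentration exceeding 50 µg/L". Section 10.7 sets the same 50 µg/L threshold on a different quantity, the end-of-treatment concentration minus the Day 0 concentration.
- **Threshold analysis (11.7.7):** "Individual observed results will also be classified as “above” or “below” the" alert threshold, using total whole blood bismuth.
- **Basis for the safety conclusion (11.7.7):** "The number of subjects requiring more than 24 hours to reach safe levels and the time required will be considered to draw conclusion".
- **Summary of categorical results (11.7.2):** "For categorical variables, the number of subjects as well as the percentage within" each category.
- **Summary of concentrations (11.7.2):** mean, median, standard deviation, minimum, maximum, coefficient of variation and confidence intervals. The confidence level is not given.
- **Eradication rate, a secondary endpoint (11.7.4.2):** "will be calculated, including a 95% confidence interval".
- **Numbers:** 200 subjects, with no sample size or power calculation (11.1). The interim is expected at 75 to 100 evaluable subjects, and the study may stop at 100 if variability is low, after the regulatory agency has been consulted (11.2).

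**The concern.** A finite sample cannot demonstrate absence; it can only put an upper limit on how common something is. The protocol decides where intervals go. It places them on the concentrations and on a secondary proportion, but names none for the proportion that bears most directly on a claim of no accumulation.

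The concentration intervals do not fill this gap. An interval on average concentration can lie far below 50 µg/L while a small fraction of subjects lies above it. The protocol's own Phase I account (1.1) shows that averages and exceedances can differ: all subjects had a Day 10 average steady-state concentration below 50 µg/L, yet 8 of 28 had sporadic blood values above it. Those were peaks of under an hour and do not predict the Day 11 result. The rationale (1.2) asks about poor compliance, misuse and concomitant medication, which is a question about unusual subjects more than about the average.

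At stake is what a result of zero may be taken to mean. No precision calculation elsewhere says what 200 subjects can exclude. Stopping at 100 would roughly double the proportion that cannot be excluded, and the planned percentage would be 0% in either case.

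**Working it through.** The protocol states no precision figure, so there is none to reproduce. The check asks what a count of zero would exclude at the sample sizes the protocol names.

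**Inputs.** n = 200 (sections 4.1 and 11.1); n = 100 (early-stop size, 11.2); n = 75 (lower end of the expected interim count, 11.2). Zero events is an assumption made for illustration.

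**Formulas.** With 0 events in n subjects, the exact (Clopper-Pearson) upper limits are:

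- two-sided 95%: 1 − 0.025^(1/n)
- one-sided 95%: 1 − 0.05^(1/n)

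**Worked example, n = 200.** Two-sided: ln(0.025)/200 = −3.6889/200 = −0.01844, so the limit is 1 − e^(−0.01844) = 1.83%. One-sided: ln(0.05)/200 = −2.9957/200 = −0.01498, so the limit is 1.49%.

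| n | Two-sided 95% upper limit | One-sided 95% upper limit | Chance of seeing zero if the true rate is 1% (0.99^n) |
|---|---|---|---|
| 200 | 1.83% | 1.49% | 0.13 |
| 100 | 3.62% | 2.95% | 0.37 |
| 75 | 4.80% | 3.92% | 0.47 |

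The one-sided limits agree with the 3/n approximation (1.5%, 3.0%, 4.0%).

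**Effect of stopping early.** 3.62/1.83 = 1.98 two-sided, and 2.95/1.49 = 1.98 one-sided. Halving the sample about doubles the proportion that zero cases leave open.

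**If one case is seen.** For 1 of 200 the percentage is 0.5% and the two-sided exact interval is 0.01% to 2.75%. For 1 of 100 it is 1% and 0.03% to 5.45%.

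**If fewer than 200 can be analysed.** The Per Protocol population (11.7.1.2) requires both blood samples and no major violation. If it held 180 subjects (an assumed figure), the two-sided limit with zero cases would be 2.03%; with 150 it would be 2.43%.

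**The 24-hour count.** Recovery time in 11.7.7 is estimated only for subjects above 50 µg/L. If none is above, none needs more than 24 hours, and with all classified subjects as the denominator the same limits apply.

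**The case against.** The strongest reply is that this is detail for the SAP. Section 11.7 promises one and declares the analysis descriptive, and the count-and-percentage sentence is a general default that also covers items such as sex. The eradication rate is categorical too and still gets an interval, so the default forbids nothing. This stands to the extent that a reader should not infer that the protocol rules an interval out; the SAP could add one. What remains is that the protocol itself allocates the intervals and names none for the proportion behind its primary question.

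A second reply is that the threshold count is not the whole answer. This is correct. Section 11.7.7 first describes the baseline-subtracted concentrations, and the above/below classification is an additional step. The reported maximum would show directly whether anyone exceeded 50 µg/L, and the standard deviation and coefficient of variation say something about spread. The closing sentence of 11.7.7 also weighs recovery time and concerns clinical safety with regard to toxicity. A reader might infer that the primary objective is decided by a bare count alone; the text does not support that. But the maximum describes only the subjects sampled and puts no limit on the proportion in the treated population.

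Third, the count is printed beside the percentage, so a careful reader can work out the limit. The early stop depends on low variability and consultation with the agency, not on a zero count. Both points are fair and limit the harm. They do not make it sensible to leave the calculation to the reader when the protocol already does it for eradication.

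**Conclusion.** The point holds as a cheap improvement. The protocol supports its safety conclusion partly by numbers of subjects and gives those numbers no interval, while giving one to the concentrations and to a secondary proportion. With zero cases the data would leave open a true proportion above 50 µg/L of up to 1.83% at 200 subjects and 3.62% at 100 (two-sided exact 95%), or 4.80% if only 75 are evaluable at the interim.

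These figures assume zero events, independent subjects, and that all n subjects can be classified. On the one-sided scale the range is 1.49% to 3.92%. The upper end of either range belongs only to a 75-subject interim and not to the stopping size of 100.

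A reader might infer that the protocol intends to treat zero observed cases as proof of absence. It does not say so. That reading comes from joining the wording of the objective to the closing sentence of 11.7.7, and it is a risk for the report, not a stated rule.

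**What to change.** In 11.7.2 and 11.7.7, state that the following are reported with an exact (Clopper-Pearson) 95% confidence interval, at the interim and at the final analysis:

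1. the proportion of subjects whose observed whole blood total bismuth is above 50 µg/L, which is the classification in 11.7.7;
2. the proportion needing more than 24 hours to reach safe levels, with all classified subjects as the denominator;
3. the proportion whose baseline-subtracted value is above 50 µg/L, if the definition in 10.7 is kept beside the one in the Synopsis.

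Word the primary conclusion by the upper limit: the data are compatible with a true proportion of up to that value. Do not word it as absence. At the interim, show the agency the limit at the current sample size next to the one expected at 200, so that the precision given up by stopping is visible.

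The cost is one extra line of analysis and one sentence of wording. No further data or visits are needed. The downside is a slightly less favourable conclusion.

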11.7.3 Analysis of Baseline and Demographic Data

Inclusion data with subject demographic information will be summarized using descriptive statistics for quantitative variables (e.g., weight, height, age) and counts and percentages for categorical variables (e.g., sex).

Additionally, subjects will be analyzed based on the method the decision to prescribe Pylera® was arrived at. This will include but not be limited to: Conduct of rapid urease test, conduct of UBT, and/or clinical evaluation.

11.7.4 Efficacy Analysis

11.7.4.1 Primary Efficacy Endpoint

Not applicable; this study is intended to assess the population PK of bismuth following treatment with Pylera®.

11.7.4.2 Secondary Efficacy Endpoints

The eradication rate of Pylera®, defined as the proportion of negative test of diagnostic *H. pylori* test (breath test, biopsy, or other test at the discretion of the Investigator) conducted at least 28 days following the end of treatment with Pylera®, will be calculated, including a 95% confidence interval. The eradication rates will be calculated for both the Safety and Per Protocol Populations.

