2.2 SECONDARY OBJECTIVES

1. To evaluate treatment effectiveness by the eradication measured by a negative diagnostic *H. pylori* test (breath test, biopsy, or other test at the discretion of the Investigator) for subjects with an initially positive *H. pylori* test.
2. To compare post-treatment bismuth concentrations in treatment successes and failures.
3. To evaluate the accumulation of bismuth in subjects receiving Pylera® with omeprazole *versus* subjects who may have received Pylera® with another proton pump inhibitor (PPI) other than omeprazole.
4. To compare population safety data profiles in treatment successes and failures.

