4.2 SELECTION CRITERIA

4.2.1 Inclusion Criteria

To be eligible, subjects must meet all of the following criteria:

#	Inclusion Criteria Description
1	Men and women 18 years of age and older who have received a prescription for Pylera® therapy from the Investigator
2	Mental and legal ability to give written Informed Consent and judged by the Investigator to be capable of following the procedures outlined within the protocol

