11.7.1.3 Safety Population

The Safety Population will be defined as all enrolled subjects who have provided informed consent.

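### The eradication rate in Section 11.7.4.2 does not require a positive pre-treatment test, although secondary objective 1 is limited to subjects who had one

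*Protocol*

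**What the plan says.** Secondary objective 1 (Protocol Section 2.2, repeated in the Synopsis) is to evaluate eradication "for subjects with an initially positive" *H. pylori* test.

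Section 11.7.4.2 describes the rate as "defined as the proportion of negative test of diagnostic" *H. pylori* testing at least 28 days after the end of treatment, and says that it "will be calculated, including a 95% confidence interval". It then names the analysis sets: "The eradication rates will be calculated for both the Safety and Per Protocol Populations". Baseline infection status is not mentioned.

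The two sets are:
- Safety (Section 11.7.1.3): "all enrolled subjects who have provided informed consent".
- Per Protocol (Section 11.7.1.2): subjects with both blood samples and no major violation or other event that could affect the PK profile.

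Eligibility does not depend on a test result. Section 4.2.1 admits adults "who have received a prescription for Pylera® therapy from the Investigator" who can consent and follow the procedures. Neither exclusion in Section 4.2.2 concerns *H. pylori* status. The Synopsis calls the study a "single-arm, open-label trial in presumed" *H. pylori*-positive subjects.

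**The concern.** The objective and the analysis section describe different denominators for the only efficacy endpoint. Under Section 11.7.4.2 as written, a subject treated on clinical grounds, never infected and negative at Day 39 is a success. Under objective 1 that subject is outside the question.

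The misclassification goes further than the rate. Objectives 2 and 4 compare bismuth concentrations and safety between treatment successes and failures, and Section 11.7.6 reports safety by those groups. The protocol gives no other definition of success, and Section 9.2.1 documents failures by a positive test at End of Study. Never-infected subjects can therefore enter only the success group.

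**Working it through.** **Is the restriction restored elsewhere?** Set side by side, the current text does not restore it:
- Section 11.5.1 captures the baseline result only where one is available.
- Section 11.7.3 expects that the decision to prescribe may rest on clinical evaluation as well as on a rapid urease or breath test.
- Section 9.1.2 records earlier tests as negative or positive, and Appendix 1 marks a diagnostic test at inclusion. Neither requires a positive result.
- Sections 11.7.1.2 and 11.7.1.3 do not mention infection.

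**Is there a figure to reproduce?** No. Section 11.1 states that no sample size or power calculation was made, and no target rate is set.

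**Bias among tested subjects.** Let e be the true rate in baseline-positive subjects and x the share of tested subjects who were never infected. Assume that all of the latter test negative.

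Rate as written = e(1−x) + x, so bias = x(1−e).

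Values of e come from the Phase III results quoted in Section 1.1. The share x is not in the documents and is assumed.

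| e | x = 5% | x = 10% | x = 20% | x = 30% |
|---|---|---|---|---|
| 93.3% | 0.05 × 0.067 = 0.3 pt | 0.10 × 0.067 = 0.7 pt | 0.20 × 0.067 = 1.3 pt | 0.30 × 0.067 = 2.0 pt |
| 87.7% | 0.05 × 0.123 = 0.6 pt | 0.10 × 0.123 = 1.2 pt | 0.20 × 0.123 = 2.5 pt | 0.30 × 0.123 = 3.7 pt |

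If real-life use gave a lower rate, the bias would grow. At an assumed e of 80% it is 2 points for x = 10% and 4 points for x = 20%.

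**Example with intervals** (200 tested, x = 20%, e about 87.7%, exact 95% limits):
- Baseline-positive only: 140/160 = 87.5% (81.4 to 92.2).
- As written: (140 + 40)/200 = 180/200 = 90.0% (85.0 to 93.8).

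**Missing follow-up tests.** Section 11.7.4.2 does not say whether the denominator is subjects tested or all members of the set. Suppose it is all members, and a share m has no test and is not counted as negative. With every subject infected, the rate is e(1−m). At e = 93.3% and m = 10% this is 0.933 × 0.90 = 84.0%.

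With both effects, and missingness unrelated to infection, the rate is (1−m)[x + (1−x)e]. It equals e when m = x(1−e)/[x + (1−x)e]:
- e = 93.3%, x = 10%: 0.0067/0.9397 = 0.7%.
- e = 87.7%, x = 20%: 0.0246/0.9016 = 2.7%.

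Under the all-members reading, even a few per cent of missing tests would offset or reverse the upward bias.

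**The case against.** **The sections can be read together.** Section 11.7.4.2 does not say that baseline-negative subjects count as eradicated. One could apply objective 1's restriction within each set, and Section 11.7 leaves detail to a SAP. That reading is available, and it softens the conflict. It does not remove it, because Section 11.7.4.2 names the populations. A SAP that follows that section departs from the objective, and one that follows the objective departs from that section.

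**The size may be small.** This stands. Pre-treatment results are scheduled for recording, so few subjects may lack a positive test. At 93.3%, the European trial's figure, the bias for x = 10–20% is 0.7–1.3 points. In the example above the interval as written has a half-width of about 4.4 points ((93.8 − 85.0)/2).

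**Nothing confirmatory depends on it.** This also stands. Section 11.7.4.1 declares no primary efficacy endpoint, the analysis is descriptive, and Section 11.7.6 rules out statistical comparisons of safety between successes and failures.

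**Stronger readings that the documents do not support:**
- *The reported rate must be too high.* This holds only among tested subjects. In the Safety set the direction depends on the unstated handling of missing tests.
- *Never-dosed subjects inflate the rate.* A subject who never started has no end of treatment from which to count 28 days, so has no qualifying test. Such subjects could enter only under the all-members reading, where they lower the rate.
- *The consent-based Safety Population is part of the same error.* It is a separate and minor matter of convention. Adverse events are collected from consent (Section 10), which fits that set, and the share never dosed is unknown.

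**Conclusion.** The point holds. Objective 1 and Section 11.7.4.2 specify different denominators, and no current text reconciles them. As written, never-infected subjects who test negative count as eradicated and join the success group in objectives 2 and 4.

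Among tested subjects the bias is upward. It is about 0.7–2.5 points for an assumed uninfected share of 10–20% and a true rate of 87.7–93.3%, and zero if every tested subject was infected. This assumes that uninfected subjects test negative. The net direction in the Safety set cannot be stated until the treatment of missing tests is fixed.

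A reader might infer that the study's main result is at risk. It is not: the primary objective concerns bismuth concentrations and does not use infection status. This is a wording correction to a secondary, descriptive endpoint, of moderate importance because it also defines the groups for two other objectives.

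**What to change.** In Section 11.7.4.2:
1. Define the eradication denominator as treated subjects with a documented positive pre-treatment *H. pylori* test, and report the rate in that set and in its Per Protocol subset.
2. State how subjects without a post-treatment test are counted, for example by giving the rate among those tested and the rate with missing tests counted as not eradicated.
3. Use the same set for the success and failure groups in objectives 2 and 4 and in Section 11.7.6.
4. Report subjects with a negative or missing baseline test in a separate descriptive line.

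No new data are needed. Section 9.1.2 already records pre-treatment tests with their results, and Section 7 records the date of first dose. The cost is a smaller denominator and a wider interval, by an amount that depends on how many subjects lack a positive baseline test. In the example above the interval width rises from 8.8 points (93.8 − 85.0) to 10.8 points (92.2 − 81.4). If prescribing on clinical evaluation alone proves common, the loss will be larger and should be shown.

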11.7.1.2 Per Protocol Population

The Per Protocol (PP) population will consist of all subjects who have met the following criteria:

- have provided 1st and 2nd blood samples for plasma and whole blood PK data;
- have completed the study without any major protocol violations or other events considered to have potential impact to the full PK profile.

Major protocol deviations include all significant deviations to the protocol related to the inclusion/exclusion criteria, to the conduct of the trial, to the subject management or assessment of safety data and may include but not limited to the following:

- conduct of any study procedure prior to the signature of the ICF
- major deviation to study procedures
- premature withdrawal from study

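### The Per Protocol eradication rate is calculated in a set built for the bismuth question: it drops validly tested subjects for a missing blood sample and does not require a positive baseline test

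*Protocol*

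**What the plan says.** Section 11.7.4.2 defines the eradication rate as the proportion of negative H. pylori tests "conducted at least 28 days following the end of treatment with Pylera®, will be calculated, including a 95% confidence interval". It then fixes the analysis sets: "The eradication rates will be calculated for both the Safety and Per Protocol Populations".

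Section 11.7.1.2 defines one Per Protocol set for the whole study. Its members must "have provided 1st and 2nd blood samples for plasma and whole blood PK data" and must "have completed the study without any major protocol violations or other events considered to have potential impact to the full PK profile". The major deviations named there include "major deviation to study procedures" and "premature withdrawal from study".

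Section 11.7.1.3 defines the Safety Population as all enrolled, consenting subjects. Section 11.7.1.1 declares an intent-to-treat population not applicable. Section 2.2 sets secondary objective 1, eradication, "for subjects with an initially positive" H. pylori test. Section 4.2.1 requires a prescription for entry but no positive test.

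**The concern.** An analysis set should be defined by what the endpoint needs. Eradication needs an infection at baseline, adequate exposure to treatment and a valid test at the right time. The 11.7.1.2 set is defined by what the bismuth analysis needs: two blood draws and the absence of "other events considered to have potential impact to the full PK profile". Using it for eradication has two consequences.

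- Subjects with a complete course and a usable test result are discarded because of a blood sample that has no bearing on whether the infection was cleared.
- Subjects who were never shown to be infected can stay in. If they test negative at the end, they count as eradicated, against the wording of secondary objective 1.

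This is more than detail left to an analysis plan. The protocol names the set, so an analysis plan that used a more suitable one would have to depart from it. What is at stake is how far the figure labelled Per Protocol can be read as an eradication rate.

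**Working it through.** The protocol states no figure to reproduce: section 11.1 says that no sample size or power calculation was made. The check is a comparison of definitions, followed by an illustration of size.

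**1. Conditions relevant to eradication, and where they appear**

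| Condition | Per Protocol set (11.7.1.2) | Safety Population (11.7.1.3) | Elsewhere |
|---|---|---|---|
| Positive baseline test | no | no | secondary objective 1 (2.2) |
| Test at least 28 days after treatment | not named | no | endpoint definition (11.7.4.2) |
| Dosing and adherence | only through the major-deviation clause | no | incorrect dosage and non-adherence are listed as deviations (11.6), not graded major or minor |
| Both bismuth draws | **yes** | no | relevant to the bismuth analyses only |
| No PK-relevant event | **yes** | no | relevant to the bismuth analyses only |

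**2. Subjects lost for a missing sample**

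Inputs: N = 200 (section 4.1) and two draws, Day 0 and Day 11. Appendix 2 takes the plasma and whole-blood tubes together at each draw, so the draw is the natural unit. Assume that a share p of subjects misses each draw, independently, and that all 200 have a valid test.

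Loss = 1 − (1 − p)²

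- p = 3%: 1 − 0.97² = 5.9%, or 11.8 of 200, about 12.
- p = 5%: 1 − 0.95² = 9.75%, or 19.5 of 200, about 20.

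If the same subjects missed both draws, the loss would be only p itself, 3-5%.

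**3. Bias**

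Let m be the share without a complete pair of draws and q their eradication rate. Let those with samples eradicate at 93%, the first trial's rate in section 1.1, used only for illustration.

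All-tested rate = 0.93(1 − m) + qm, so the Per Protocol excess = m(0.93 − q).

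With m = 10%:

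- q = 93%: all tested 93.0%, excess 0.
- q = 80%: 0.9 × 93 + 0.1 × 80 = 91.7%, excess 1.3 points.
- q = 60%: 0.9 × 93 + 0.1 × 60 = 89.7%, excess 3.3 points.

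**4. Precision**

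Exact 95% intervals near 93%:

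- 186/200: 88.5% to 96.1%, width 7.6 points.
- 167/180: 88.0% to 96.1%, width 8.1 points.

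Losing 20 subjects costs little precision.

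**5. Uninfected subjects**

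Let u be the share uninfected at baseline, all testing negative at the end, and e the true eradication rate in the infected (both assumptions).

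Apparent rate = e(1 − u) + u, so the inflation = u(1 − e).

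- e = 93%, u = 5%, 10% or 20%: 0.35, 0.7 or 1.4 points.
- e = 80%, same u: 1, 2 or 4 points.

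This inflation affects both reported rates, because neither set requires baseline infection.

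**The case against.** The case against has real substance.

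- **Timing and dosing are not ignored.** A reader might infer that nothing about infection, dosing or test timing qualifies a subject. The documents do not support that. The 28-day minimum is in the endpoint definition, and major dosing, adherence or procedure deviations can exclude a subject through 11.7.1.2 read with 11.6. Which of them are major may properly be left to the analysis plan. Only the baseline-infection condition is absent altogether.
- **The subjects are not lost to the study's eradication results.** They stay in the Safety Population rate. This stands, and it limits the consequence. That rate does not repair the point, however: it requires neither treatment nor a positive baseline test.
- **Selective loss is a weak argument.** One might argue that subjects who miss Day 11 are poor adherers, so the Per Protocol rate is flattered. Any ordinary per-protocol set removes poor adherers too. Subjects who stop early follow section 9.2.2, which lists no bismuth sample, so the sample condition acts partly as a course-completion filter. The 3.3 points are a what-if, not a demonstrated error.
- **The loss can be overstated.** Treating the four specimens (plasma and whole blood at two draws) as independently missing at 3-5% gives 1 − 0.97⁴ = 11.5% to 1 − 0.95⁴ = 18.5%. Tubes from one draw tend to be missed together, so that range is not a fair reading.
- **Comparability with earlier trials.** A reader might infer that the rate cannot be set beside the 93% and 87.7% quoted in section 1.1. The protocol does not say which analysis sets gave those figures and plans no comparison, so nothing can be concluded.

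None of this removes the core: a stated rule excludes valid eradication results for a reason unrelated to eradication, and neither set carries the infection condition of objective 1.

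**Conclusion.** The point holds, as a set-definition fault of modest size. The Per Protocol eradication rate is conditioned on bismuth sampling and on PK-relevant events, and neither reported rate is restricted to subjects with a positive baseline test, as secondary objective 1 requires.

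At an assumed 3-5% of subjects missing each draw, independently, about 12-20 of 200 leave the Per Protocol rate. The bias from this is zero if they eradicate like the rest, and reaches about 3.3 points only if 10% are missing and they eradicate at 60% against 93%. The missing-sample shares, the eradication rates and the uninfected share are all assumptions; the protocol gives none of them for this study. The endpoint is secondary and descriptive, and the primary bismuth objective is untouched. The change is worth making because the rule is explicit and cheap to correct, not because a study conclusion depends on it.

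**What to change.** In section 11.7.4.2, replace the Per Protocol set by an eradication-evaluable set with three conditions:

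1. an initially positive H. pylori test, in line with secondary objective 1;
2. a stated treatment-exposure criterion, based on the compliance data already recorded;
3. a valid H. pylori test at least 28 days after the end of treatment.

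State that bismuth samples and PK-relevant events play no part in this set. Report how many subjects had no baseline test result, since section 11.5.1 collects it only where available. Keep the 11.7.1.2 set for the bismuth analyses, including secondary objective 2, which compares bismuth concentrations in successes and failures and does need the samples.

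The cost is one definition. Dose dates, premature discontinuation and whether all doses were taken (section 7), baseline tests with results (9.1.2) and the eradication test (9.2.1) are already recorded in the study.
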